15.3.3. CLASI

The CLASI assesses activity of disease and damage done by the disease in 13 anatomical locations [Klein, 2011]. These locations are:

- Scalp
- Ears
- Nose
- Rest of face
- V-area of neck (frontal)
- Posterior neck and/or shoulders
- Chest
- Abdomen
- Back, buttocks
- Arms
- Hands
- Legs
- Feet

To calculate the CLASI activity score, the numeric scores of each anatomical location for degree of erythema (0=absent, 1=pink; faint erythema, 2=red, or 3=dark red; purple/violaceous/hypertonic) are added to the responses for mucous membrane lesions (0=absent, 1=lesion or ulceration), recent hair loss (0=no, 1=yes), and non-scarring alopecia (0=absent, 1=diffuse; non-inflammatory, 2=focal or patchy in one quadrant, 3=focal or patchy in more than one quadrant). The CLASI activity score ranges from 0 to 70.

To calculate the CLASI damage score the total numeric scores for dyspigmentation (0=absent, 1=dyspigmentation) for the 13 anatomical locations is calculated. If the response to the dyspigmentation duration question indicates that dyspigmentation usually lasts for at least 12 months, the total dyspigmentation score is multiplied by two. The resulting dyspigmentation score is added to the sum of the scarring scores (0=absent, 1=scarring, 2=severe) for all locations except for the scalp. Scalp scarring, scored as part of the alopecia assessment with possible values of 0=absent, 3=one quadrant, 4=two quadrants, 5=3 quadrants, or 6=whole skull, is then added to compute the total damage score. The CLASI damage score ranges from 0 to 56.

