3.1.2. Secondary Efficacy Endpoints

Secondary efficacy endpoints are provided below:

- Annualized flare rate by British Isles Lupus Assessment Group (BILAG)-2004 flare index through Day 169 all flares
- Time-to-first flare by BILAG-2004 flare index
- Achievement of Lupus Low Disease Activity State (LLDAS) at Day 169
- Change from baseline in Systemic Lupus Erythematosus Disease Activity Index 2000 (SLEDAI-2K) total score at Day 169
- Cumulative prednisone-equivalent dose use (total area under the curve of daily prednisone-equivalent dose) through Day 169
- Achievement of ≥50% reduction in Cutaneous Lupus Erythematosus Disease Area and Severity Index (CLASI) activity score at Day 169 in the subgroup of subjects with baseline CLASI activity score ≥8

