6.17. Cutaneous Lupus Erythematosus Disease Area and Severity Index Activity Score

The CLASI activity score is calculated by adding the numeric values of the responses to items in the erythema, scale/hypertrophy categories, the mucous membrane involvement question, questions about acute hair loss and non-scarring alopecia. The scores for affected body parts are weighted equally regardless of surface area and number of lesions present. More severe manifestation within an area is scored higher then less severe manifestation.

6.18. 50% Improvement in CLASI Activity Score

A 50% reduction in CLASI activity score compared to baseline defined by meeting all of the following criteria:

• Achieve ≥50% reduction from baseline in CLASI activity score at Day 169

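### SAP 15.3.3 leaves scale/hypertrophy out of the CLASI activity score, contradicting SAP 6.17 and its own 0–70 range

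*SAP*

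**What the plan says.** SAP 3.1.2 lists as a secondary endpoint a reduction of at least 50% in CLASI activity score at Day 169, "in the subgroup of subjects with baseline CLASI activity score ≥8". SAP 6.18 and the estimand table in SAP 7.7 carry the same endpoint.

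The score is described in two places:

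- **SAP 6.17** obtains it by "adding the numeric values of the responses to items in the erythema, scale/hypertrophy categories, the mucous membrane involvement question", together with the acute hair loss and non-scarring alopecia questions. It gives no numeric codings.
- **SAP 15.3.3** gives the codings. It states that "The CLASI assesses activity of disease and damage done by the disease in 13 anatomical locations" and sets out the sum starting "To calculate the CLASI activity score, the numeric scores of each anatomical location for degree of erythema". To erythema it adds mucous membrane lesions, recent hair loss and non-scarring alopecia. Scale/hypertrophy is not mentioned. The paragraph closes with "The CLASI activity score ranges from 0 to 70".

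**The concern.** The two sections define one score with different components, and the appendix formula cannot reach the maximum that its own paragraph states. Section 15.3.3 is the only text with item values, so whoever programs the derivation has to use it.

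The score both selects the analysis subgroup and decides response within it. Leaving out a non-negative component can only lower the baseline score, so at a fixed cutoff of 8 the subgroup can shrink but not grow. Response is a ratio, so dropping a component can turn a responder into a non-responder or the reverse. Enrolment stopped at 76 subjects in two arms (SAP 4.1), so the subgroup may be small and a few reclassifications could matter.

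**Working it through.** **Inputs, all from SAP 15.3.3**

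| Item | Range | Source |
|---|---|---|
| Anatomical sites | 13 | "The CLASI assesses activity of disease and damage done by the disease in 13 anatomical locations" |
| Erythema, per site | 0–3 | "degree of erythema (0=absent, 1=pink; faint erythema, 2=red, or 3=dark red; purple/violaceous/hypertonic" |
| Mucous membrane; recent hair loss | 0–1 each | "mucous membrane lesions (0=absent, 1=lesion or ulceration), recent hair loss (0=no, 1=yes" |
| Non-scarring alopecia | 0–3 | "non-scarring alopecia (0=absent, 1=diffuse; non-inflammatory, 2=focal or patchy in one quadrant, 3=focal or patchy in more than one quadrant" |
| Stated range of activity score | 0–70 | "The CLASI activity score ranges from 0 to 70" |

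**Step 1. Try to reproduce the stated maximum.** The maximum is the sum of the item maxima:

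13 × 3 + 1 + 1 + 3 = 39 + 5 = **44**, against 70 stated. The figure is not reproduced. The gap is 70 − 44 = 26, and 26 / 13 = 2 points per site.

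**Step 2. Check the method on the damage score in the same section.** Dyspigmentation is 0–1 at 13 sites, doubled if long-lasting; scarring is 0–2 at the 12 non-scalp sites; scalp scarring goes up to 6:

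13 × 1 × 2 + 12 × 2 + 6 = 26 + 24 + 6 = **56**, which equals the stated maximum of 56. The method works, so the shortfall is specific to the activity formula.

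**Step 3. Put back the component named in SAP 6.17.** The documents do not give the coding of scale/hypertrophy, so it is assumed here:

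| Assumed coding per site | Maximum activity score |
|---|---|
| 0–1 | 44 + 13 = 57 |
| 0–2 | 44 + 26 = **70** |
| 0–3 | 44 + 39 = 83 |

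Of these, only 0–2 gives the stated 70.

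**Step 4. What the choice of formula does.** These subjects are hypothetical, with all other items at zero:

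| Subject | SAP 15.3.3 | SAP 6.17 |
|---|---|---|
| (a) Baseline erythema 6, scale 3 | 6: outside the subgroup | 6 + 3 = 9: inside |
| (b) Erythema 8 to 4, scale 4 to 4 | 8 to 4, 50.0% reduction: responder | 12 to 8, 33.3%: non-responder |
| (c) Erythema 8 to 5, scale 4 to 1 | 8 to 5, 37.5%: non-responder | 12 to 6, 50.0%: responder |

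**Step 5. Leverage of one subject.** The documents give no subgroup count. If there were 5 to 15 subgroup subjects per arm (an assumption), one reclassified responder would move that arm's rate by 1/5 = 20 to 1/15 = 6.7 percentage points.

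**The case against.** The best reply is that the intended score is not really in doubt. SAP 3.1 sends the reader to Section 6 for efficacy endpoint definitions, 6.17 names every component, and the 0–70 range rules out the shortened sum. On that view the appendix has a drafting slip, and a careful programmer would notice that the total falls short. Programming may already follow 6.17.

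The stakes are also limited. The 26 points are a ceiling, reached only with maximal scale at every site. The example subjects are invented, and the documents give no baseline CLASI distribution. Only one secondary endpoint, in a subgroup, is affected. The primary objective is safety, and SRI-4 and BICLA (SAP 6.5 and 6.6) do not use CLASI.

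Most of this stands as a limit on size: the intent can be inferred, and the consequences are possible rather than shown. It does not remove the fault. Section 6.17 has no item values, so it cannot be programmed without 15.3.3. The coding of the missing item appears nowhere in the SAP, and no rule says which section prevails. A sponsor that follows 6.17 would still have to complete 15.3.3.

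**Conclusion.** The concern holds. As written, SAP 15.3.3 gives an activity score with a maximum of 44 rather than 70, omits a component that 6.17 includes, and so gives a different score for any subject with scale/hypertrophy. The loss is at most 26 of 70 points (26 / 70 = 37%) for one subject. It can remove subjects from the baseline ≥8 subgroup and can change response status in either direction.

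The conflict rests on the SAP's own text and arithmetic. The 0–2 coding per site is inferred from the 26-point gap and is not stated anywhere. The number of subjects affected cannot be computed from the documents. The point should be corrected because the score governs both entry to and response in a named secondary endpoint; the primary efficacy endpoints are unaffected.

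**What to change.** In SAP 15.3.3, add scale/hypertrophy, scored at each of the 13 sites, to the activity formula and state its numeric coding. The coding should be confirmed against the instrument as collected; 0–2 per site makes the formula agree with 6.17 and sum to 70. Then confirm that the derivation program uses the full score for both the baseline ≥8 flag and the Day 169 response.

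The cost is one sentence in the appendix and one program check. If the programming already follows 6.17 with the right coding, no results change.

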15.3.4. SLICC/ACR Damage Index

The SLICC/ACR Damage Index (SDI) measures non-reversible change occurring since the onset of SLE and present for at least six months in 12 different organ systems. A total of 39 items within 12 organ systems are scored as 0, indicating no damage, or ≥1, indicating damage, for a max total score of 47. The SDI organ systems, items and their possible scores are shown in Table 12.

Table 12: SLICC/ACR Organ Systems and Items

Organ System	Item Name	Score
Ocular	Any cataract ever	0, 1
	Renal change or optic atrophy	0, 1
Neuropsychiatric	Cognitive impairment	0, 1
	Seizures requiring therapy ≥6 months	0, 1
	CVA ever (score 2 if >1)	0, 1, 2
	Cranial or peripheral neuropathy	0, 1
	Transverse myelitis	0, 1
Renal	eGFR <50%	0, 1
	Proteinuria ≥3.5 gm/24 hr	0, 1
	End-stage renal disease	3
Pulmonary	Pulmonary hypertension	0, 1
	Pulmonary fibrosis	0, 1
	Shrinking lung	0, 1
	Pleural fibrosis	0, 1
	Pulmonary infarction	0, 1
Cardiovascular	Angina or coronary artery bypass	0, 1
	Myocardial infarction ever (score 2 if>1)	0, 1, 2
	Cardiomyopathy	0, 1
	Valvular disease	0, 1
	Pericarditis or pericardiectomy	0, 1
Peripheral Vascular	Claudication ≥6 months	0, 1
	Minor tissue loss	0, 1
	Significant tissue loss (score 2 if >1 site)	0, 1, 2
	Venous thrombosis or venous stasis	0, 1
Gastrointestinal	Infarction or resection of bowel (score 2 if >1 site)	0, 1, 2
	Mesenteric insufficiency	0, 1
	Chronic peritonitis	0, 1
	Stricture or upper GI surgery ever	0, 1

Organ System	Item Name	Score
Musculoskeletal	Atrophy or weakness	0, 1
	Deforming or erosive arthritis	0, 1
	Osteoporosis with fracture or vertebral collapse	0, 1
	Avascular necrosis (score 2 if >1 site)	0, 1, 2
	Osteomyelitis	0, 1
Skin	Scarring chronic alopecia	0, 1
	Extensive scarring or panniculum	0, 1
	Skin ulceration	0, 1
Premature gonadal failure		0, 1
Diabetes		0, 1
Malignancy (score 2 if >1 site)		0, 1, 2

Source: Gladman, 1996.

Notes: CVA=Cerebrovascular accident; eGFR=Estimated glomerular filtration rate; GI=Gastrointestinal

15.3.5. FACIT – Fatigue

The scoring of the Functional Assessment of Chronic Illness Therapy-Fatigue (FACIT-F) is based on guidelines published by the FACIT group [FACIT, 2003]. The following steps are required to score the FACIT-F.

- 1. The 13 questions constituting the FACIT fatigue assessment are identified by unique item code numbers. Possible responses for each item are 0="not at all", 1="a little bit", 2="somewhat", 3="quite a bit", or 4='very much".
- 2. The reported item responses for each question are converted to a final score by subtracting the reported response from the reversal factor for the specified item listed in Table 13. For example, if a subject's response to item HI7, "I feel fatigued", is 4 (very much), the item score is equal to 0 (4-4).
- 3. The resulting item scores are added to derive a total score.
- 4. The total score is multiplied by the number of items in the subscale (n=13 for FACIT-F).
- 5. Finally, the result of step 4 is divided by the number of items answered to obtain the final FACIT-F score.

The resulting FACIT – F scores range from 0 to 52 with a higher score indicating a better quality of life. The final score will be used for all analyses of FACIT – F data.

Table 13: FACIT – Fatigue Item Scoring

FACIT Item Code	Item Reversal Factor	Valid Resulting Item Scores
HI7	4	4, 3, 2, 1, 0
HI12	4	4, 3, 2, 1, 0
An1	4	4, 3, 2, 1, 0
An2	4	4, 3, 2, 1, 0
An3	4	4, 3, 2, 1, 0
An4	4	4, 3, 2, 1, 0
An5	0	0, 1, 2, 3, 4
An7	0	0, 1, 2, 3, 4
An8	4	4, 3, 2, 1, 0
An12	4	4, 3, 2, 1, 0
An15	4	4, 3, 2, 1, 0
An16	4	4, 3, 2, 1, 0

Source: FACIT, 2003.

Notes: FACIT=Functional Assessment of Chronic Illness Therapy.

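### Step 2 of the FACIT-F scoring rule gives negative scores for items An5 and An7, contradicting Table 13 and the stated 0 to 52 range

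*SAP*

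**What the plan says.** SAP 15.3.5 sets out five steps. Step 1 gives each of the 13 items a response from 0 to 4. Step 2 converts each response by "subtracting the reported response from the reversal factor for the specified item", with the factors given in Table 13. Its only worked example is HI7, an item with factor 4: if the response "is 4 (very much), the item score is equal to 0 (4-4"). Step 3 sums the item scores. Step 4 reads: "The total score is multiplied by the number of items in the subscale (n=13 for FACIT-F"). In step 5, "the result of step 4 is divided by the number of items answered to obtain the final FACIT-F score".

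Table 13 then lists, for each item, a reversal factor and the valid resulting scores. An5 and An7 have factor 0 and valid scores 0, 1, 2, 3, 4. The other ten visible items have factor 4 and valid scores 4, 3, 2, 1, 0.

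The section closes with: "The resulting FACIT – F scores range from 0 to 52 with a higher score indicating a better quality of life". It adds that this final score feeds every FACIT-F analysis.

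**The concern.** Step 2 is a single rule for all items, and it works only where the factor is 4. Where the factor is 0, subtracting the response gives zero or a negative number. Neither step 2 nor any other part of the section makes an exception for factor-0 items, and the worked example does not reach them. The instruction therefore disagrees with two other statements in its own section: the valid-score column and the range with its direction.

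This text serves as the programming specification. SF-36 scoring is left to vendor software (SAP 15.3.7), but the FACIT-F steps are spelled out for the analyst. The protocol collects FACIT-F at eight visits (Days 1, 29, 57, 85, 113, 141, 169 and 197) and presents patient-reported outcomes, including fatigue, as adding to the disease activity assessments (Protocol 4.4.4). If step 2 were coded as written, two items would run backwards in every total. Because the error depends on the responses, it would not generally cancel in change from baseline.

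**Working it through.** **Inputs (all from SAP 15.3.5).** Response r = 0 to 4 for each item. Literal step 2: item score = factor - r. Visible rows of Table 13: ten with factor 4 (HI7, HI12, An1, An2, An3, An4, An8, An12, An15, An16) and two with factor 0 (An5, An7). Total = sum of item scores x 13 / items answered.

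**Assumption.** The section says 13 items, but 12 rows are visible. The main calculation gives the thirteenth item factor 4, so 11 items have factor 4 and 2 have factor 0. The 12-row variant is shown alongside.

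**1. The stated range, using Table 13's valid scores.**
- 13 items: minimum 13 x 0 = 0; maximum 13 x 4 = 52.
- 12 visible rows, prorated: minimum 0; maximum 12 x 4 x 13/12 = 52.

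The valid-score column reproduces 0 to 52 either way.

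**2. Literal step 2 for An5 and An7.** 0 - r gives 0, -1, -2, -3, -4, against 0, 1, 2, 3, 4 in Table 13.

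**3. Range under literal step 2.**

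| Case | Minimum | Maximum |
|---|---|---|
| 13 items (11 + 2) | 11 x 0 + 2 x (-4) = -8 | 11 x 4 + 2 x 0 = 44 |
| 12 visible rows (10 + 2), prorated | -8 x 13/12 = -8.67 | 40 x 13/12 = 43.33 |
| An5 and An7 both unanswered | 0 | 44 x 13/11 = 52 |

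The stated range survives only in the last case, where neither affected item contributes.

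**4. Best and worst answers, 13 items.** The best answer is response 0 on factor-4 items and 4 on An5 and An7. Literal: 11 x 4 - 2 x 4 = 36. Table 13: 11 x 4 + 2 x 4 = 52. The worst answers score 0 under both.

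**5. Size of the error.** With all 13 items answered, intended total minus literal total = (An5 + An7) - (-(An5 + An7)) = 2 x (An5 + An7), where An5 and An7 are the responses. The maximum is 2 x (4 + 4) = 16. One extra response point on either item moves the total by -1 instead of +1.

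**6. Effect on a treatment difference.** Let R be the group difference from the 11 factor-4 items and S the difference from An5 and An7 together, both in intended scores. The intended difference is R + S; the literal difference is R - S.
- R and S of the same sign: the difference is attenuated, and reverses sign if S is larger than R in size.
- S = 0: unchanged.
- R and S of opposite sign: enlarged.

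As an illustration only, if every item improved by the same amount d, the intended difference would be 13d and the literal one 11d - 2d = 9d, a loss of 4/13, about 31%. The documents give no item-level figures from which to estimate R and S.

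**The case against.** The strongest reply is that the right scores are already in the section. Step 2 sends the programmer to Table 13, whose valid-score column, read against responses 0 to 4, gives the intended value for every listed item. The stated range and direction agree with it, and the section says its scoring follows published guidelines for the instrument. A literal coding would also produce negative item scores, outside the table's own list, so ordinary checking should catch it. All of this stands, and it makes an unnoticed error less likely. It does not remove the contradiction, because a specification should not leave the programmer to choose between its rule and its table.

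A reader might infer more than the documents support:
- That 0 to 52 cannot be reached at all. It can, by using the valid-score column, or when An5 and An7 are both unanswered.
- That any treatment difference on fatigue would shrink. That requires the two items to move with the rest (working, point 6).
- What An5 and An7 ask. The SAP does not print their wording. That they run in the favourable direction is inferred from factor 0, valid scores 0 to 4 and "scores range from 0 to 52 with a higher score indicating a better quality of life".
- That Table 13 omits an item. The twelfth and last visible row may only mean that one was lost when the PDF was read, so this is not counted as a defect.

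It is also fair to say that the consequence is small. FACIT-F is absent from the primary and secondary efficacy endpoints in SAP 3.1 and from the estimands in SAP Table 2, and it plays no part in the sample size. The visible SAP names no specific FACIT-F analysis, although some text is redacted.

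**Conclusion.** The point holds as an internal contradiction in SAP 15.3.5. Step 2, applied as written, gives An5 and An7 scores of 0 to -4, in conflict with Table 13 and with the stated range and direction.

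The finding for these two items rests on the visible text alone. The -8 to 44 range and the score of 36 for the best answers also assume that the thirteenth item has factor 4. The 12-row variant differs only slightly and leads to the same conclusion. The 16-point maximum error applies when all 13 items are answered.

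This is a minor point. It concerns FACIT-F summaries only. The documents do not show that any result would be wrong, since they do not say how the score was programmed, and Table 13 points to the correct coding.

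**What to change.** Replace the single rule in step 2 with two: items with reversal factor 4 are scored as 4 minus the response; items with reversal factor 0 (An5 and An7) are scored as the response itself. This matches Table 13 and restores 0 to 52. A second worked example for An5 or An7 would remove any doubt.

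Before FACIT-F outputs are produced, confirm in the scoring program that every item score lies between 0 and 4 and every total between 0 and 52.

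The cost is one sentence in an SAP appendix and a short program check. No data collection, endpoint definition or sample size changes.

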15.3.6. Tender and Swollen Joint Count

For each of 14 anatomical regions, i.e., locations, the presence of tender, swollen or tender and swollen joints is recorded. These values are collected separately for the left and right sides of the body, i.e., laterality, yielding 28 values.

Three separate joint count scores (Tender, Swollen and Tender/Swollen) will be derived as follows for each visit:

- If the status variable in the record states "Intentionally left blank", all joint counts are set to missing for that visit.
- For each location and laterality, if the result contains "Tender", add 1 to the tender joint count.
- For each location and laterality, if the result contains "Swollen", add 1 to the swollen joint count.
- For each location and laterality, if the results contains "Tender|Swollen", add 1 to the tender/swollen joint count.

Results reported as "NA" will not be counted in the total joint count. Responses of "NA" will be displayed in the data listing with the reason given for this response.

15.3.7. SF-36

The Short Form Health Survey -36 (SF-36) is a general health patient-reported outcome survey containing 36 items. Individual items on the SF-36 have different numbers of valid responses. Scores are calculated for the eight subscales and two component scales by transforming responses to a 0 to 100 scale. Higher scores indicate better health. Scoring will be performed using the vendor software.

15.4. Randomization Algorithm

Subjects enrolled in this study were randomly assigned to receive either ALPN-101 or placebo in a 1:1 ratio. Randomization was stratified by geographic region and by use of concomitant oral immunosuppressant therapy at enrollment using a centralized interactive web-based response system.

Geographic regions include the following:

- Geographic region 1: Sites located in North America or Western Europe
- Geographic region 2: Sites located in Eastern Europe
- Geographic region 3: Sites in Asia

15.5. Laboratory Assessments

All per-protocol laboratory assessments will be performed by the central lab per the assessment schedule shown in Table 14. Investigators must document their review of each laboratory safety report.

Table 14: Clinical Laboratory Assessments

Assessment	Parameters
Safety:	Platelet count
Hematology	RBC count and indices: MCV, MCH, percent reticulocytes
	WBC count with differential; neutrophils, lymphocytes, monocytes, eosinophils, basophils
	Absolute neutrophil count and lymphocyte count; CD4 and CD8 lymphocytes
	Hemoglobin
	Hematocrit
Safety:	Electrolytes: sodium, potassium, chloride, bicarbonate
Clinical Chemistry	Other cations: calcium, magnesium, phosphorus
	Amylase
	Lipase
	Glucose
	CPK
	LDH
	Renal function: creatinine, eGFR
	Liver Function Tests: ALT, albumin, alkaline phosphatase, AST, total and direct bilirubin, total protein
Safety: Coagulation	PT (i.e., INR), aPTT
Safety: Urinalysis	Specific gravity, pH, glucose, protein, blood, ketones, bilirubin, urobilinogen, nitrite, leukocyte esterase, microscopic examination if blood or protein is abnormal, UPCR
Infectious Disease	Hepatitis B and C viruses, Human Immunodeficiency Virus, tuberculosis, SARS-CoV-2
Other Tests	TSH, FSH and estradiol (female subjects only, if needed to confirm menopausal status)
Clinical Biomarkers of SLE	Screening only: ANA, anti-Smith antibodies, anti-SSA antibodies, anti-SSB antibodies, anti-RNP antibodies, Scl 70 (topoisomerase 1) antibodies, centromere antibodies, anticardiolipin antibodies (IgG and IgM), LAC, anti-beta-2-glycoprotein I antibodies All applicable visits: hsCRP, complements (C3, C4, CH50), quantitative IgM, IgG, IgA, IgE, dsDNA antibodies

Notes:

ALT=Alanine aminotransferase; ANA=Anti-nuclear antibodies; aPTT=Activated partial thromboplastin time; AST=Aspartate aminotransferase; C3=Complement component 3; C4=Complement component 4; CD=Cluster of differentiation; CH50=Total complement; CPK=Creatinine phosphokinase; dsDNA=Double stranded DNA eGFR=Estimated glomerular filtration rate; FSH=Follicle stimulating hormone; hsCRP=High-sensitivity C-reactive protein; INR=International normalized ratio; LAC=Lupus anticoagulant; LDH=Lactate dehydrogenase; MCH=Mean corpuscular hemoglobin; WBC=White blood cell; MCV=Mean corpuscular volume; PT=Prothrombin time; RBC=Red blood cell;

RNP=Ribonucleoprotein; Ig=Immunoglobulin; SSA=Sjögren's syndrome type A; SSB=Sjögren's syndrome type B; TSH=Thyroid stimulating hormone; UPCR=Urine protein-creatinine ratio.

